### 3 GENERAL STATISTICAL CONSIDERATIONS

As this study is an extension study, some of the patient data are only collected in the I10E-1302 study (e.g. demography). The necessary information for the analyses of this study are obtained by combining the necessary information from the database of I10E-1302 and I10E-1306. The details about which data are to be taken from I10E-1302 are given in the respective analyses within this Statistical Analysis Plan (SAP).

#### 3.1 DESCRIPTION OF VARIABLES

Continuous data will be described using number of valid observations, number of missing observations, mean, standard deviation, median, quartiles, minimum and maximum.

Categorical data will be described using number of missing observations, number of valid observations per category and percentage. Number of missing observations will not be taken into account for the calculation of percentages.

For descriptive statistics, the following number of decimal places (dps) will generally be applied:

- 3 dps for values in [0, 0.9995)
- 2 dps for values in [0.9995, 9.995)
- 1 dp for values in [9.995, 99.95)
- 0 dp for values  $\geq 99.95$

For negative values the same rule will be followed using the absolute value.

For original case report form (CRF) variables the minimum and maximum will use to the same number of dps as the raw data. Statistics on count variables (e.g. number of infusions) will generally be presented with 1 dp while the minimum and maximum will be presented without dp. Percentages will be presented with 1 dp. Exceptions from these rules might be applied when necessary.

#### 3.2 HANDLING OF MISSING DATA AND OUTLIERS

Regarding the primary criterion, a patient will be also considered as a non-responder if the patient is withdrawn due to lack of efficacy of the treatment (insufficient response to the investigational medicinal product [IMP]). If the INCAT score at EOS visit is missing, then the Last Observation Carried Forward (LOCF) approach will be applied and the last available adjusted INCAT disability score will replace the missing value at EOS visit.

The LOCF approach will also be used to handle the missing data of secondary endpoints.

When AEs are documented in the diary, date-time of AE onset may be missing or incomplete. As a result, it might not be possible to determine if the AE started between the start of an infusion until 72 hours after the end of the infusion (Temporally Associated AE [TAAE]). In such cases, the response to the question "Did the

AE start within 72 hours of an infusion” will be used for determining if the AE is temporally associated to an infusion or not.

Partial dates of first symptoms and partial dates of diagnosis (collected in the I10E-1302 study) will be imputed by 15 if only the day is unknown and by 1st July if day and month are unknown. No imputation will be done if the year is unknown.

For the calculation of duration of AEs, partial start and end dates will be imputed with the first and last possible date within the period defined by the partial date, respectively. In general, no calculation of duration will be made if either the start date or stop date is missing, i.e., can't be imputed using pre-determined rules.

No other general rules for the replacement of missing data are planned.

Data listings will always show the original CRF reported values and not the imputed values.

### 3.3 HANDLING OF LOCAL LABORATORY DATA

Given that local laboratories were utilized for the study, laboratory results standardization may be utilized. This will proceed as follows. Denote by  $R_U$  and  $R_T$  the untransformed result and transformed result, respectively, and  $(I_L, I_H)$  and  $(S_L, S_H)$  are the investigators' and standard lower and upper limits of normality, respectively, then the transformed laboratory result can be derived using the expression

$$R_T = S_L + \frac{R_U - I_L}{I_H - I_L} (S_H - S_L).$$

Note that conversion to SI units of the untransformed result will precede the standardization process. The transformed result will be used for descriptive summaries and displays for observed and change values. If standardization is not utilized, then the untransformed result will be used for descriptive summaries and displays for observed and change values. In either case, summaries and displays for laboratory categories such as abnormalities based on L (below LLN), N (between LLN and ULN) and H (above ULN) classifications will use the classifications based on the untransformed result.

Final decision on laboratory results standardization will be made prior to database lock and will be contingent on the evaluation of the sparseness of laboratory data, the completeness of the local laboratories' normal ranges, and the choice of the standard normal ranges.

### 3.4 MULTIPLICITY ISSUES, SUBGROUP ANALYSIS, INTERIM ANALYSIS, BLINDING AND RANDOMISATION

This study is purely descriptive and no hypotheses are tested. No multiplicity issues are present.

No subgroup analyses and no interim analyses are planned.

Likewise, blinding and randomisation is not applicable in this single-arm trial.

### 3.5 DEFINITION OF THE PROTOCOL DEVIATIONS AND POPULATIONS

#### 3.5.1 Populations

The definition of analysis sets is as follows:

- Total Treated Set (TTS): all patients who received at least one administration of the study drug.
- Full Analysis Set (FAS): all TTS patients having an available assessment of the primary efficacy criterion.
- Per Protocol Set (PPS): all FAS patients without any major deviations from protocol.

If a patient is treated with a non-permitted treatment during the study period, specifically those that confound efficacy evaluation, then all efficacy variables measured after the intake of these not-allowed treatments will be censored for the efficacy analyses. Censoring of measurements will be done up to a reasonable window from the start time of a prohibited treatment where the window is determined according to the half-life of the not- allowed treatment. The window will be adjudicated prior to database lock.

The TTS will be used for the analysis of safety data.

The FAS will be used for the primary analysis of efficacy data and the PPS to test its robustness.

#### 3.5.2 Protocol Deviations

The protocol deviations and corresponding categories are defined in the protocol deviation specifications as well as their consequence for the inclusion in the different analysis sets. The following protocol deviations categories will be studied:

- Deviations regarding inclusion criteria
- Deviations regarding exclusion criteria
- Deviations regarding the study drug
- Deviations regarding safety assessments
- Deviations regarding assessment of laboratory parameters (including biomarkers)
- Deviations regarding visit windows
- Deviations regarding informed consent
- Deviations regarding forbidden treatments during the study

- Deviations regarding overdose/misuse of study drug
- Other deviations
- Deviations regarding the primary efficacy endpoint
- Deviations regarding other efficacy endpoints
- Deviations regarding exploratory endpoints
- Deviations regarding the ancillary study
- Deviations regarding study material

In addition to these protocol deviations, other protocol deviations may be reported by the clinical research associate (CRA).

All the protocol deviations which occurred during the study will be examined during the final data review meeting. All adjudicated protocol deviations will be presented in data listings.

#### 4 STATISTICAL ANALYSIS

##### 4.1 DISPOSITION OF PATIENTS

In order to describe the population, descriptive statistics (number, or number and percentages) will be provided for the following:

- Patients screened (patients who signed informed consent)
- Patients enrolled
- Patients with a screening failure
- Patients who received study treatment (TTS)
  - Patients participating in the ancillary study
  - Patients who completed the study
  - Patients withdrawn early from the study and reasons for study discontinuation [AE, Protocol deviation, Withdrawal of consent, Lost to follow-up, Insufficient response to IMP, Other]  
Patients withdrawn early due to insufficient response of IMP with reason for insufficient response (INCAT, MRC sum score, R-ODS, Grip strength, CGI-Patient, CGI-Investigator, Clinical examination, Premature termination of IMP) and follow-up treatment (IVIg, Corticosteroids, Immunomodulatory or immunosuppressive agent or Other)
- Patients included in the FAS
- Patients included in the PPS

A separate in-text summary table will be produced to contain the following information: patients who received at least one dose of IMP in I10E-1302; non-responders in I10E-1302; responders in the study; and patients who discontinued. An in-text listing with all patients who were discontinued due to "Insufficient response to the IMP" may be produced. The said listing will contain identifiable relapse risk information based on review of efficacy and safety information.

Except for patients enrolled and patients with a screening failure, percentages will be calculated using the number of patients of the TTS as the denominator. For screen failure patients, a listing will be produced with the reason for screening failure and the specifications provided by the investigator. For patients who discontinued the study, a listing will be produced with the reasons of study discontinuation and the specifications provided by the investigator.

#### 4.2 PROTOCOL DEVIATIONS

The absolute number of deviations as well as the number and percentage of patients with at least one protocol deviations will be tabulated by deviation category and by the classification into Minor/Major. Deviation details will be provided in a listing.

#### 4.3 DEMOGRAPHIC AND BASELINE CHARACTERISTICS

Unless otherwise specified, the baseline value is defined as the last available value before the first IMP course in I10E-1306. The baseline value might therefore come either from the last visit in the I10E-1302 study or the first visit in the I10E-1306 study.

The following characteristics will be summarized in subjects of the TTS. If the FAS significantly differs from the TTS, the characteristics will also be summarized on the FAS.

| Parameter   | Data origin |
|--|--------------------|
| • Demographic characteristics: Age (years), Gender, Race, and Ethnicity (if collected) | I10E-1302          |
| • Clinical examination:  |                    |
| ○ Weight (kg), Height (cm) and Body Mass Index (kg/m  )                    | I10E-1302          |
| • History of CIDP disease:   |                    |
| ○ Time since the date of first symptoms  | I10E-1302          |
| ○ Time since the date of diagnosis   | I10E-1302          |
| ○ Time between first symptoms and diagnosis  | I10E-1302          |
| ○ Diagnostic categories of CIDP  | I10E-1302          |
| ○ Clinical criteria of CIDP (typical / atypical)                                       | I10E-1302          |

- Electrophysiological criteria of definite CIDP I10E-1302
- Supportive criteria of CIDP I10E-1302
- Current INCAT disability score (arms, legs and global non-adjusted INCAT scores and global adjusted INCAT score) I10E-1306
- Prior medications
  - Prior medications will be presented by therapeutic subgroup (level 2) and chemical subgroup (level 4) according to version WHO\_DDE\_B2\_DECEMBER\_1\_2014 of the World Health Organization's (WHO) Anatomical Therapeutic Chemical (ATC) classification system. I10E-1302  
The term “prior medication” refers to any prior medication of the I10E-1302 study plus all concomitant medication given during the I10E-1302 study which ended before the first visit of the I10E-1306 study.
- Medical and surgical history
  - Medical and surgical history will be classified by PT and SOC using the version 17.1 of the Medical Dictionary for Regulatory Activities (MedDRA). I10E-1302  
The term “Medical and surgical history” refers to any medical and surgical history of the I10E-1302 study plus all adverse events which occurred in the I10E-1302 study.

A listing of prior CIDP treatment(s) since diagnosis [e.g., intravenous Ig (IVIg), subcutaneous Ig (SCIg), corticosteroids, and immunomodulatory or immunosuppressant agents] will be produced. The listing information will include patient status (naïve/in relapse), dosing information (start/stop times, duration, time since last dose), and reason for stopping (as applicable). As subsequent treatment periods with IVIg, corticosteroids and immunomodulatory or immunosuppressant agents might be reported under the category *Other* in the CRF, the reported treatments in this category will be classified into IVIg, corticosteroids, immunomodulatory or immunosuppressant agents and other. A listing with other treatments and their duration will be presented.

#### 4.4 CONCOMITANT TREATMENTS

Prior medications are any medications the patient received up to 8 months before screening or judged relevant by the Investigator. Thus, a prior medication is defined as a medication with a date of screening  $\leq$  start date + 8 months. If a medication has a partial start date, the earliest possible date within the partial date is used.

Concomitant medications are any medications the patient received at any time during the study, i.e. from screening to EOS visit. Thus a concomitant medication is defined as a medication with a treatment period which has at least one day in common with the period date of screening to EOS visit, i.e.

- Date of screening  $\leq$  Start date of medication  $\leq$  Date of EOS visit or

- Date of screening  $\leq$  End date of medication  $\leq$  Date of EOS visit or
- Start date of medication  $\leq$  Date of screening and Date of EOS visit  $\leq$  End date of medication

If a medication has a partial start date or end date, the earliest possible date within the partial start date is used and the last possible date within the partial end date.

Prior and concomitant medications will be summarized using TTS and will be classified according to version WHO\_DDE\_B2\_DECEMBER\_1\_2014 of the WHO ATC classification system. Separate tables will be produced for prior and concomitant medications presenting the number and percentage of patients with at least one medication by therapeutic subgroup (level 2) and chemical subgroup (level 4). The tables will be sorted by decreasing incidence of therapeutic subgroup and by decreasing incidence of chemical subgroup within therapeutic subgroup.

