## **7. PRIOR AND CONCOMITANT MEDICATION**

### **7.1. Prior Medication**

The term ‘prior medication’ refers to any medication given up to 8 months before study entry, i.e. 2 months before informed consent is signed.

All relevant prior medications taken within 8 months prior to the study entry must be recorded in the patient’s medical file and documented on the appropriate pages of the CRF. Moreover, any prior medication taken more than 8 months prior to the study which is, in the opinion of the investigator, clinically relevant to the patient's condition will also be recorded.

The following prior medications are not allowed before patient inclusion because they could interfere with the assessment of study drug efficacy:

- Any other investigational product administered within a month prior to screening of PRISM I10E-1302 study.
- Exposure to blood products or derivatives within 3 months prior to screening of PRISM I10E-1302 study
- Immunomodulators/immunosuppressors agents (including but not limiting to cyclophosphamide, cyclosporine, interferon- $\alpha$ , interferon- $\beta$ 1a, anti-CD20, alemtuzumab, aziathioprine, etanercept, mycophenolate mofetil and methotrexate) or haemopoetic stem cell transplantation. administered during the last 12 months prior to screening of PRISM I10E-1302 study.
- Systemic corticosteroids therapy, if administered with an increasing dosage or introduced, or administered at a dose higher than 10 mg prednisolone per day, or equivalent within the last 3 months prior to screening of PRISM I10E-1302 study. Topical corticosteroids are permitted.
- Loop diuretics administered during the last 24 hours hours before IVIg infusion planned date. In this case, the study drug infusion date will have to be postponed.
- Study drug at another dosage than planned in this study: 0.5 g/kg.

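### The date inequality for prior medication in SAP 4.4 does not implement its own definition, has no upper limit, ignores end dates, and differs from SAP 4.3

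*SAP*

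**What the plan says.** SAP 4.4 opens with a definition in words: "Prior medications are any medications the patient received up to 8 months before screening or judged relevant by the Investigator". It then gives the rule to be programmed: "Thus, a prior medication is defined as a medication with a date of screening" less than or equal to "start date + 8 months". The only supporting date convention concerns the start: "If a medication has a partial start date, the earliest possible date within the partial date is used".

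For concomitant medication, the same section uses a different construction: "a medication with a treatment period which has at least one day in common with the period date of screening to EOS visit". That rule uses both start and end dates, is bounded at screening and EOS, and has a partial-date convention for each end.

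SAP 4.3 plans a summary of prior medication on the same set (TTS), at the same ATC levels and with the same dictionary version. It defines the term differently, as any prior medication of I10E-1302 "plus all concomitant medication given during the I10E-1302 study which ended before the first visit of the I10E-1306 study".

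Protocol 7.1 defines prior medication by exposure: "any medication given up to 8 months before study entry, i.e. 2 months before informed consent is signed". It also asks for older medication to be recorded where the Investigator considers it clinically relevant.

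**The concern.** The words in SAP 4.4 (*received*) and Protocol 7.1 (*given*) describe exposure during a window. The inequality tests only when a drug was started, and only from one side. A programmer who follows it would build a prior-medication table that contradicts the sentence it is meant to implement. On-study drugs could enter the table, and long-running drugs taken in the window could be left out.

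The two SAP sections also give one summary two definitions that cannot both be met. In addition, SAP 4.4 does not say whether screening means that of I10E-1302 or of I10E-1306.

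**Working it through.** The plan has no figure to reproduce here, so the check is the algebra and a set of test histories.

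**Algebra.** Screening ≤ start + 8 months is the same as start ≥ screening − 8 months. Start has no upper bound, and the end date does not appear.

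**Partial dates.** Taking the earliest possible start widens an overlap rule. Under this inequality it does the reverse, because an earlier start is more likely to fail the lower bound.

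**Which screening.** Protocol 7.1 equates 8 months before study entry with 2 months before consent. The difference, 8 − 2 = 6 months, matches the initial 6-month treatment in I10E-1302. The 8-month window therefore fits an anchor at entry to I10E-1306. If I10E-1302 screening were meant, the window would open about 8 + 6 = 14 months before entry. Either reading leaves the upper bound and the end-date test missing.

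**Test histories.** Assumptions: I10E-1306 screening is day 0; EOS is week 48; I10E-1302 screening is 24 weeks earlier; and I10E-1302 prior medication reaches back 2 months before that. The last assumption follows Protocol 7.1, because the I10E-1302 protocol is not available. The relevance clause is left out, since the inequality does not carry it. The rules compared are:

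- 4.4 inequality: start ≥ screening − 8 months.
- 4.4 sentence: start < screening and end ≥ screening − 8 months.
- 4.3: I10E-1302 prior medication, or I10E-1302 concomitant medication that ended before V1.
- Concomitant: the SAP 4.4 overlap with screening to EOS.

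| History (relative to screening) | 4.4 inequality | 4.4 sentence | 4.3 | Concomitant |
|---|---|---|---|---|
| A: start −4 months, stop −2 months | yes | yes | yes | no |
| B: start −2 months, ongoing | yes | yes | no | yes |
| C: start week 20, stop week 21 | yes | no | no | yes |
| D: start week 47, ongoing | yes | no | no | yes |
| E: start −24 months, stop −1 month | no | yes | yes | no |
| F: start −24 months, ongoing | no | yes | yes | yes |
| G: start −9 months, stop −7 months | no | yes | yes | no |
| H: start after EOS | yes | no | no | no |

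**Results.**

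- The inequality disagrees with its own sentence in 6 of 8 histories (C to H) and with 4.3 in 7 of 8 (B to H).
- C and D are classed as both prior and concomitant.
- E and G appear in neither SAP 4.4 table.
- F is missed as prior but still appears as concomitant.
- An overlap rule matching the sentence agrees with 4.3 in 7 of 8. The exception is B, a drug started during I10E-1302 and ongoing at V1, which 4.3 does not count as prior.

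The histories were chosen to probe the rule, so these counts are not expected frequencies. H shows the missing bound; such a drug may never be recorded.

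**The case against.** The strongest reply is that the intent is clear and practice may protect the table. The sentence before the inequality is sound. SAP 4.3 gives I10E-1302 as the data origin for prior medication, and under its definition a drug started during I10E-1306 cannot be prior. Separate databases or CRF pages might keep on-study drugs out. This stands as far as it goes: no program is visible, so a reader should not infer that every on-study drug will in fact be tabulated as prior. But SAP 4.4 states its own derivation without that restriction, and SAP section 3 says information from both databases is combined.

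Two stronger readings are tempting, and the documents support neither.

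- *Stable low-dose corticosteroids would be lost.* If taken during the study, they meet the concomitant rule. SAP 4.3 also plans a listing of CIDP treatments since diagnosis, with start and stop times and no 8-month limit.
- *Rescue treatment would be obscured.* Relapsing patients have their EOS assessments before other CIDP treatment and are then withdrawn (Protocol 3.1.6 and 5.4). Follow-up treatment after insufficient response is reported in disposition (SAP 4.1). Assessments after forbidden treatment are flagged in listings (SAP 4.6).

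The relevance clause can also bring some older drugs back, although the inequality omits it.

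**Conclusion.** The point holds as a drafting error with limited reach. Read literally, the SAP 4.4 inequality does not implement its own definition or Protocol 7.1, and it conflicts with SAP 4.3. The drugs that can drop out of both SAP 4.4 tables are those started more than 8 months before screening, stopped before screening, taken in between within the window, and not brought back by the relevance clause. Any that were CIDP treatments would still be in the SAP 4.3 listing.

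Only the descriptive prior-medication table is affected. The response, relapse, censoring and adverse-event rules do not use the prior-medication flag.

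The missing bound and missing end date rest on the text alone. The comparison with 4.3 also rests on the assumed timing and content of I10E-1302 prior medication. How many patients would be misclassified cannot be judged from the documents.

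**What to change.** Replace the inequality with a bounded overlap rule of the kind SAP 4.4 already uses for concomitant medication. A drug is prior if either of these holds:

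- its start date is before I10E-1306 screening, and its end date is missing, ongoing, or on or after I10E-1306 screening minus 8 months; or
- the Investigator judged it relevant, which Protocol 7.1 provides for with medication older than the window.

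State that screening means I10E-1306 screening, in line with the 8 months before study entry in Protocol 7.1. Apply to the end date the partial-date convention already given for concomitant medication. Use the same definition in SAP 4.3, and say there whether drugs started during I10E-1302 and ongoing at V1 are shown as prior, concomitant or both.

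The cost is short edits to SAP 4.3 and 4.4 and one changed programming condition. No new data are needed.
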